Selinexor	Take with at least 120 mL (4 ounces) of fluids (water, juice, etc.)	Tablet*	Oral	Days 1,8, and 15 of each cycle *	
*Doses/schedule as appropriate for assigned dose level.					

**Patients continuing on ibrutinib should take ibrutinib days 1-28 of Cycle 1

Dose Level	Selinexor Dose	Selinexor Schedule	Ibrutinib Dose	Ibrutinib Schedule
1*	40 mg	Weekly (oral)	420 mg	Daily (oral)
2	20 mg	Bi-weekly (oral)	420 mg	Daily (oral)

For the phase I study, an adaptive dose finding design using a modified continuous reassessment method will be followed. Once the MTD of selinexor in combination with ibrutinib is identified, an expansion cohort of up to 10 CLL patients and 10 lymphoma patients will be accrued to better describe the toxicity profile, evaluate feasibility of pharmacodynamics studies, and to gain additional efficacy data. Dose-limiting toxicity (DLT) will be assessed during cycle 1 only. Provided the patient does not experience significant toxicity, patients may continue treatment until disease progression. Response will be assessed by PET/CT, CT, and/or peripheral blood immunophenotyping every 3 cycles during the 1st year of therapy and then every 6 months until disease progression or as medically indicated. PET/CT is preferred in lymphoma patients. In patients with bone marrow involvement at the start of therapy, a bone marrow biopsy will be performed to confirm a complete response (CR). Additionally, bone marrow biopsy will be performed at 1 year and then yearly provided other criteria for CR exist.

Definition of DLT for patients receiving selinexor and ibrutinib*	
General	

 Treatment delays >28 days for any toxicity Any grade 5 toxicity 	
Non-hematologic	

 Grade 3 nausea/vomiting or diarrhea lasting for ≥ 7 days while taking optimal supportive medications# Grade 3 anorexia or fatigue lasting for ≥ 7 days while taking optimal supportive care# and with correction of dehydration, anemia, endocrine, or electrolyte abnormalities Grade ≥ 3 AST or ALT elevation lasting for ≥ 7 days OR any Grade ≥ 3 AST or ALT elevation in the setting of bilirubin elevation $> 2 \times$ ULN Any other Grade 3 non-hematological toxicity except alopecia, rash that resolves to Grade 1 in ≤ 7 days, or electrolytes abnormalities correctable with supportive therapy# Any Grade 4 non-hematologic toxicity not specifically listed above 	
Hematologic	

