- l. Reassessment off therapy will occur 4 weeks from the last dose of study therapy. For patients removed from study for reasons other than disease progression, reassessment will then occur then every 6 months until progression or an alternative therapy is started.
- m. Cycle 2 Day 1 only.
- n. Cycle 4 Day 1 only.
- o. Restaging scans and immunophenotyping will be performed every 3 cycles for the first year and then every 6 months thereafter.
- p. Bilateral bone marrow biopsies are preferred for lymphoma patients.
- q. A bone marrow biopsy and aspirate should be performed to confirm a complete response if there was bone marrow involvement at diagnosis, clinical MRD flow should be performed in this case.
- r. For patients with DLBCL only: Paraffin block must be submitted for immunohistochemistry evaluation of CD10, bcl-6, and MUM-1 to determine ABC vs GCB subtype. Biopsy to confirm histologic review does not need to be repeated for pre-study requirements, so long as previously obtained tissue confirms patient meets histologic eligibility criteria prior to study registration.

OSU Protocol #:14087

Version 7

Date: 03 August 2021

Cohort 3 Study

Calendar

Cycle	Pre-Study	Day 1, Cycles 1-3	Day 1, Cycles 6, 9, 12	Cycle 14 Day 1	Day 1, every 3 cycles following cycle 14 (continue ibrutinib) C17, 20, 23, 26, etc.	Day 1, every 3 cycles following cycle 14 (off therapy)	Follow-up (off therapy) ^j
Eligibility checklist	X						
Informed consent	X						
History ^a	X						
Progress note ^b		X	X	X	X	X	X
Physical exam	X	X	X	X	X	X	X
Ophthalmologic exam ^c	X						
Concurrent meds	X	X	X		X		
Vital signs/weight/height/BSA	X	X	X		X	X	
ECOG ^d	X	X	X		X	X	
CBC, dif, platelets	X	X	X		X	X	
Coagulation ^e	X	X	X		X		
Chemistry ^f , Ca, Mg, Phos	X	X	X		X	X	
Liver function tests ^g	X	X	X		X		
LDH	X						
Uric acid	X						
Peripheral blood immunophenotyping	X		X			X	X
Quant immunoglobulins	X		X				
SPEP with immunofixation							

CLL karyotype, FISH panel ^h & IgVH mutational analysis ^h	X						
Pregnancy test ⁱ	X						
HIV/Hep	X						
Buccal swab	X						
ECG	X						
Adverse event evaluation	X	X			X		
PET/CT or CT scans	X					X ^k	X
Bone marrow biopsy and aspirate	X			X			
Correlative studies	X	X	X	X	X	X	

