- a. Initial medical history should include: baseline symptoms; a detailed history of prior cancer therapies including start and stop dates, disease progression during or after therapy, as well as discontinuations due to intolerability or any other serious illness; family and social history; calculation of Rai Stage (for CLL patients)
- b. Progress notes should include: new symptoms or adverse events, ECOG performance status (Appendix A), documentation of physical exam, status of disease.
- c. Ophthalmologic exam: required at screening and if clinically indicated during study. Prior to dilation: best corrected visual acuity, visual field examination via automated perimetry, tonometry, and color vision test. Dilated funduscopy and slit lamp exam including anterior segment photos to document lens clarity.
- d. For ECOG performance status, see Appendix A
- e. Prothrombin time, international normalization ratio, and activated partial thromboplastin time
- f. Sodium, potassium, bicarbonate, BUN, calcium, chloride, creatinine
- g. Albumin, alkaline phosphatase, total bilirubin, total protein, SGOT [AST], SGPT [ALT]
- h. Only if not done prior to initiation of ibrutinib
- i. Pregnancy tests for females of childbearing potential. A female of childbearing potential (FCBP) is a sexually mature female who: 1) has not undergone a hysterectomy or bilateral oophorectomy; or 2) has not been naturally postmenopausal (amenorrhea following cancer therapy does not rule out childbearing potential) for at least 24 consecutive months (i.e., has had menses at any time in the preceding 24 consecutive months). Female of childbearing potential must have a negative serum β -

Hcg pregnancy test result within 3 days of first study dose.

- j. Reassessment off therapy will occur 4-6 weeks from the last dose of study therapy. For patients removed from study for reasons other than disease progression, reassessment will then occur then every 6 months until progression or an alternative therapy is started.
- k. Restaging scans and immunophenotyping will be performed every 3 cycles for the first year and then every 6 months thereafter.

Bilateral bone marrow biopsies are preferred for lymphoma patients.

- l. A bone marrow biopsy and aspirate should be performed to confirm a complete response if there was bone marrow involvement at diagnosis, clinical MRD flow should be performed in this case.

	1															2	Q3 Cycles	Relapse
Day	1							2	8	15						16	1	1

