11.1.2 Response Criteria for NHL

Definition of Response for NHL Patients: Criteria for response will utilize the IWG Response Criteria for NHL patients⁴².

Complete Response (CR):

Complete disappearance of all detectable clinical evidence of disease and disease related symptoms if present before therapy.

- In patients with no pre-treatment PET scan, or if the PET scan was positive before therapy, a post-treatment residual mass of any size is permitted as long as it is PET-negative.
- The spleen and/or liver, if considered enlarged prior to therapy on the basis of a physical examination or CT scan, should not be palpable on physical examination and should be considered normal size by imaging studies, and nodules related to lymphoma should disappear. However, determination of splenic involvement is not always reliable because a spleen considered normal in size may still contain lymphoma, whereas an enlarged spleen may reflect variations in anatomy, blood volume, the use of hematopoietic growth factors, or causes other than lymphoma.
- If the bone marrow was involved by lymphoma before treatment, the infiltrate must have cleared on repeat bone marrow biopsy. The biopsy sample on which this determination is made must be adequate (with a goal of > 20 mm unilateral core). If the sample is indeterminate by morphology, it should be negative by immunohistochemistry. A sample that is negative by immunohistochemistry, but that demonstrates a small population of clonal lymphocytes by flow cytometry, will be considered a CR until data become available demonstrating a clear difference in patient outcome.

Partial Response (PR):

- At least a 50% decrease in the sum of the product of the diameters (SPD) of up to six of the largest dominant nodes or nodal masses. These nodes or masses should be selected prior to initiation of therapy according to all of the following: a) they should be clearly measurable in at least two perpendicular dimensions; b) if possible, they should be from disparate regions of the body; and c) they should include mediastinal and retroperitoneal areas of disease whenever these sites are involved.
- No increase should be observed in the size of other nodes, liver, or spleen.
- Splenic and hepatic nodules must regress by $\leq 50\%$ in their SPD, or, for single nodules, in the greatest transverse diameter.

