- With the exception of splenic and hepatic nodules, involvement of other organs is usually assessable and no measurable disease should be present.
- Bone marrow assessment is irrelevant for determination of a PR if the sample was positive before treatment. However, if positive, the cell type should be specified (e.g., large-cell lymphoma or small neoplastic B cells). Patients who achieve a CR by the above criteria, but who have persistent morphologic bone marrow involvement, will be considered partial responders. When the bone marrow was involved before therapy and a clinical CR was achieved, but with no bone marrow assessment after treatment, patients should be considered partial responders.
- No new sites of disease should be observed.
- If performed, the post-treatment PET should be positive in at least one previously involved site.

Stable Disease (SD):

Patient fails to attain the criteria needed for a CR or PR, but does not fulfill those for progressive disease (see below). If performed, the PET should be positive at prior sites of disease, with no new areas of involvement on the post-treatment CT or PET.

Progression (PD) or Relapse:

- Lymph nodes should be considered abnormal if the long axis is > 1.5 cm, regardless of the short axis. If a lymph node has a long axis of 1.1 to 1.5 cm, it should only be considered abnormal if its short axis is > 1.0 . Lymph nodes ≤ 1.0 by ≤ 1.0 will not be considered as abnormal for relapse or progressive disease.
- Appearance of any new lesion > 1.5 cm in any axis during or at the end of therapy, even if other lesions are decreasing in size. Increased FDG uptake in a previously unaffected site should only be considered relapsed or progressive disease after confirmation with other modalities. In patients with no prior history of pulmonary lymphoma, new lung nodules identified by CT are mostly benign. Thus, a therapeutic decision should not be made solely on the basis of the PET without histologic confirmation.
- At least a 50% increase from nadir in the SPD of any previously involved nodes, or in a single involved node, or the size of other lesions (e.g., splenic or hepatic nodules). To be considered progressive disease, a lymph node with a diameter of the short axis of $<$

1.0 cm must increase by $\geq 50\%$ and to a size of 1.5 x 1.5 cm, or > 1.5 cm in the long axis.

- At least a 50% increase in the longest diameter of any single previously identified node > 1.0 cm in its short axis.

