11.1.3 Response Criteria for CLL Patients

Definition of Response for CLL Patients: Criteria for response will utilize the IWCLL Response criteria¹⁴.

Complete response (CR):

CR requires all of the following criteria as assessed at least 2 months after completion of therapy:

- Peripheral blood lymphocytes (evaluated by blood and differential count) below $4 \times 10^9/L$ ($4000/\mu L$). The presence of minimal residual disease (MRD) after therapy should be assessed. The sensitivity of the method used to evaluate for MRD should be reported.
- Absence of significant lymphadenopathy (e.g., lymph nodes > 1.5 cm in diameter) by CT scan of the abdomen, pelvis, and thorax.
- No hepatomegaly or splenomegaly by physical examination.
- Absence of constitutional symptoms.
- Blood counts above the following values:
 - Neutrophils more than $1.5 \times 10^9/L$ ($1500/\mu L$) without need for exogenous growth factors.
 - Platelets more than $100 \times 10^9/L$ ($100\,000/\mu L$).
 - Hemoglobin more than 110 g/L (11.0 g/dL) without red blood cell transfusion or need for exogenous erythropoietin.
- A marrow aspirate and biopsy should be performed at least 2 months after the last treatment and if clinical and laboratory results as above demonstrate that a CR has been achieved.
 - To define a CR, the marrow sample must normocellular for age, with less than 30% of nucleated cells being lymphocytes. Lymphoid nodules should be absent. If lymphoid nodules are present then these nodules should be recorded as nodular PR. However, immunohistochemistry should be performed to define whether these nodules are composed primarily of T cells or lymphocytes other than CLL cells or of CLL cells. If the marrow is hypocellular, a repeat determination should be performed after 4 weeks, or until peripheral blood counts have recovered. However, this time interval should not exceed 6 months after the last treatment. A marrow biopsy should be compared with that of pretreatment marrow. The quality of the CR should be assessed for MRD by flow cytometry or by immunohistochemistry (IHC).

CR with incomplete marrow recovery (CRi):

All the criteria for a CR (including the marrow examination) have been met though there is persistent anemia or thrombocytopenia or neutropenia apparently unrelated to CLL but related to drug toxicity.

Partial response (PR) PR is defined as follows:

- A decrease in the number of blood lymphocytes by 50% or more from the value before therapy.

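### Calendar footnote q ties the marrow that confirms CR to involvement at diagnosis, in conflict with the synopsis and Section 11, so some CRs in Cohorts 1 and 2 may go unconfirmed or be confirmed late

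*Combined protocol and SAP*

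**What the plan says.** The documents state when a marrow is needed to confirm CR in four places.

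- **Section 10, general calendar, footnote q.** A marrow is done to "confirm a complete response if there was bone marrow involvement at diagnosis, clinical MRD flow should be performed in this case". Every post-baseline marrow cell in this calendar (Cycles 4-6, Cycles 7+, follow-up) carries footnote q.
- **Synopsis (treatment schema ahead of the table of contents).** "In patients with bone marrow involvement at the start of therapy, a bone marrow biopsy will be performed to confirm a complete response (CR"). The next sentence adds a second route: "bone marrow biopsy will be performed at 1 year and then yearly provided other criteria for CR exist".
- **Section 11.1.2 (NHL).** For CR, "If the bone marrow was involved by lymphoma before treatment, the infiltrate must have cleared on repeat bone marrow biopsy". Under PR, the section deals with a clinical CR in a patient whose marrow was involved before therapy: "with no bone marrow assessment after treatment, patients should be considered partial responders".
- **Section 11.1.3 (CLL).** All listed criteria must be met for CR. One is a marrow aspirate and biopsy, to be done "if clinical and laboratory results as above demonstrate that a CR has been achieved", with no condition on earlier involvement.

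The Cohort 3 calendar repeats the diagnosis wording in its footnote l ("A bone marrow biopsy and aspirate should be performed to confirm a complete response if there was bone marrow involvement at diagnosis"), but no cell in that table cites footnote l. Its Cycle 14 Day 1 marrow carries no condition.

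**The concern.** Sites schedule procedures from the calendar, and the calendar's trigger refers to a different time from the one the response criteria use. Section 3.1.1 requires at least one prior therapy in Cohorts 1 and 2, so diagnosis may lie well before study entry and marrow status may have changed. Section 10 already requires a pre-study marrow within 45 days of registration. The status that Section 11.1.2 needs is therefore known, but footnote q does not use it.

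At stake is the split between CR and PR. Section 13.8.2 plans to summarise degree of response by disease group and dose level, and Section 2.10 gives deeper remission as part of the rationale. A missing marrow can only turn a CR into a PR, never the reverse, so any error understates depth of response.

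**Working it through.** **1. The plan's own CR-dependent figure.** The only numerical rule that depends on CR is in Section 13.2: at least 3 MRD-negative CRs among 10 Cohort 3 patients. The formula is P(X ≥ 3) = 1 − Σ(k = 0 to 2) C(10,k) p^k (1−p)^(10−k). At p = 0.30 this is 1 − (0.0282 + 0.1211 + 0.2335) = 0.617. For true rates 0.1, 0.2, 0.25, 0.3, 0.35 and 0.4 the results are 0.0702, 0.3222, 0.4744, 0.6172, 0.7384 and 0.8327. All agree with the plan's table. The figures do not change with footnote wording, because the Cycle 14 marrow is scheduled for every Cohort 3 patient.

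**2. The triggers side by side, Cohorts 1 and 2, for a patient who otherwise meets CR.**

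| Patient | Footnote q | Synopsis confirmatory marrow | Section 11 |
|---|---|---|---|
| NHL, clear at diagnosis, involved pre-study | not triggered | required | needed; PR if absent (written) |
| NHL, involved at diagnosis, clear pre-study | triggered | not required | not needed |
| NHL, involved at both | triggered | required | needed |
| CLL/SLL, clear at diagnosis, involved pre-study | not triggered | required | needed |
| CLL/SLL, clear at both | not triggered | not required | needed |
| CLL/SLL, involved at diagnosis | triggered | depends on pre-study marrow | needed |

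The first row loses its marrow only if the site works from footnote q and overlooks the synopsis and Section 11.1.2. In the fifth row neither footnote q nor the synopsis confirmatory rule asks for the marrow that Section 11.1.3 requires; the 1-year marrow is the only scheduled route. So the synopsis does not fully match the CLL criteria either.

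**3. Effect on the CR rate.** Section 13.1 allows up to 10 patients per disease group in the expansion. One CR recorded as PR changes the rate by 1/10 = 10 points. Exact 95% intervals show the scale:

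- 3/10: 6.7% to 65.2%
- 2/10: 2.5% to 55.6%
- 1/10: 0.3% to 44.5%
- 0/10: 0% to 30.8%

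**4. Effect on ORR.** Section 13.5.2 counts CR and PR alike as response. If, for illustration, 6 of 10 respond, ORR stays 60% (26.2% to 87.8%) however the 6 divide.

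**5. Effect on duration of CR.** Section 11.1.4 starts the clock when CR criteria are first met. Suppose clinical CR is seen at Cycle 4 Day 1, 3 × 28 = 84 days after the start, and the marrow waits for the 1-year visit. The recorded CR then starts up to 365 − 84 = 281 days late. This is an illustration that takes the marrow date as the date CR is met.

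**The case against.** The strongest reply is that nothing in footnote q forbids a marrow. The synopsis requires one in any patient, NHL or CLL, who is involved when therapy starts, which is exactly the NHL patient at risk. Its 1-year and yearly marrow does not depend on earlier involvement and so reaches the CLL/SLL patients too, if they are still followed. Section 11 itself asks for the marrow. This stands, and it limits the harm: a CR is missed or delayed only where a site follows the calendar alone. It does not remove the conflict, because the yearly marrow has no calendar entry of its own and a late marrow still moves the date of CR.

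Three stronger readings are tempting, and the documents do not support them.

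- A reader might infer that true CRs cannot be scored and default to PR in both diseases. Other routes to a marrow exist, and the PR default is written only for NHL; for CLL it is an inference from the CR definition.
- A reader might infer that the Cohort 3 decision rule is at risk because footnote l repeats the wording. The unconditional Cycle 14 marrow protects it.
- A reader might multiply an assumed share of patients with changed marrow status by an assumed CR rate to get a percentage misclassified. The documents give no such share, and only changes from clear to involved could matter in NHL. The background CR figures are also mostly low: 2 of 25 in ABC DLBCL (Section 2.5) and none among 68 patients on selinexor (Section 2.9), against 3 of 9 in MCL (Section 2.4).

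It is also fair to say that Section 11.1.3 places the CLL CR assessment at least 2 months after therapy ends, while Cohorts 1 and 2 are treated until progression. Read literally, that is a wider obstacle to scoring CLL CRs. It is a separate matter, and aligning the marrow trigger does not resolve it.

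**Conclusion.** The contradiction is real and operational, because footnote q governs every post-baseline marrow in the Cohort 1 and 2 calendar. Its reach is small: the descriptive CR/PR split and the duration of CR in those cohorts, always toward fewer or later CRs. The DLT primary endpoint, ORR and the Cohort 3 rule are untouched.

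The size is 10 points of CR rate per affected patient in a group of 10. The number affected is unknown. It depends on how many patients were clear at diagnosis and on whether sites also work from the synopsis and Section 11. This is an inconsistency worth correcting, not a threat to the trial's main conclusions.

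**What to change.** Reconcile the passages to one trigger that matches Section 11.

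- **Footnote q:** replace *at diagnosis* with *on the pre-study marrow*, and add *and in every CLL/SLL patient otherwise meeting CR criteria*.
- **Synopsis:** use the same wording, so that it also agrees with Section 11.1.3.
- **General calendar:** list the 1-year and yearly marrow that the synopsis already calls for.
- **Cohort 3 footnote l:** align the wording for consistency only.

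The cost is a few lines of text. No procedure is added beyond those the synopsis and Section 11.1.3 already call for, and the pre-study marrow is already collected. There is one small loss: NHL patients involved at diagnosis but clear at entry would no longer have the confirmatory marrow and MRD flow that footnote q now triggers.
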